The sample size for this study is calculated using G-power 3.1.9.7 statistical software to determine the effect size. According to Cohen (1988), effect sizes are categorized as large (0.80), medium (0.50), and small (0.20). Since most research results have an effect size of 0.50, this study sets the criterion of at least a medium effect size. With α =0.05, statistical power (power)=0.80, and effect size set at 0.5, the estimated sample size is 60 individuals. Considering potential changes in the elderly or refusal to participate, a dropout rate of 15% is estimated. Therefore, a total of 70 elderly individuals from community-based activities will be recruited for this study. The inclusion criteria for this study are as follows: (1) aged 65 and above, (2) able to communicate in Mandarin or Taiwanese and willing to complete interviews or self-administered questionnaires, (3) no mobility impairments (e.g., stroke, Parkinson's disease, motor neuron diseases), (4) no severe cardiovascular diseases, (5) no degenerative joint diseases or acute attacks in the past three months, (6) lower limb joint surgery performed more than three months ago, and (7) no dizziness or any unstable health conditions that hinder exercise. During the study period, participants who do not engage in physical

activity for more than three weeks or have missing pre-test or post-test data will be excluded from the statistical analysis.

Ethical Considerations:

Prior to conducting the study, the research proposal will be submitted to the Institutional Review Board (IRB) for review and approval. Approval was obtained from the Taipei Medical University Joint Institutional Review Board (TMU-JIRB) on November 24, 2022, with the approval letter numbered N202210004 (see Appendix 1). This study aims to investigate the effects of VR interactive games as part of exercise prescriptions on the balance function and lower limb strength of elderly participants.

Section 3: Intervention Tools

Hardware Setup:

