After data collection, the collected data will be coded, documented, and analyzed using the Statistical Package for the Social Sciences (SPSS) 19.0 Chinese version software. Both descriptive and inferential statistics will be employed. A significance level of p < .05 will be used to determine statistical significance.

1. Descriptive Statistics:

Categorical variables of demographic data for both experimental and control groups will be presented as percentages, while continuous variables will be described using means and standard deviations.

2. Inferential Statistics:

(a) Independent t-test or Mann-Whitney U test:

Analyze the differences between the experimental and control groups in variables such as balance function, muscle strength, flexibility, cardiovascular capacity, and quality of life befor intervention. A Shapiro-Wilk test will be conducted to check for normal distribution. If the data is normally distributed, an independent t-test will be used; otherwise, the Mann-Whitney U test will be employed.

(b) Chi-Squared Test:

Analyze the homogeneity of basic demographic characteristics (age, gender, education level, marital status), exercise habits, duration of each exercise session, and experience of falling in the past year between the two groups.

(c) Dependent Samples t-test or Wilcoxon Signed Rank Test: Analyze the differences in variables such as balance function, muscle strength, flexibility, cardiovascular capacity, and quality of life within each group 之前 and after the intervention. A Shapiro-Wilk test will be conducted to check for normal distribution. If the data is normally distributed, a dependent samples t-test will be used; otherwise, the Wilcoxon signed rank test will be employed.

(d) ANCOVA Analysis using Intention-to-Treat Analysis:

ANCOVA will be employed to compare the post-test scores between the experimental and control groups while controlling for pre-test scores. This analysis will utilize intention-to-treat principles.

[figure not shown]

Figure 8. Flowchart of the application of virtual reality interactive games

to the lower limb balance of community elders

Research Results

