This study involved the intervention of the experimental group using virtual reality interactive games, while the control group underwent exercise interventions led by original instructors. Both groups participated in modal rate-intensity sessions three times a week for 12 weeks, totaling 36 sessions. Testing was conducted befor and three months after the completion of the program. A total of 84 participants were recruited from two community care activity centers in Taipei City, but 14 participants were excluded due to personal reasons or inability to consistently monitor data due to illness. Ultimately, data from 70 participants who completed at least 30 sessions were analyzed.

Regarding participant attrition, the experimental group initially recruited 35 participants. However, during the 12-week, 36-session program, five participants were absent for over one-third of the sessions (12 sessions) due to health issues or personal preferences, rendering their data unusable. The experimental group experienced a dropout rate of 14.28%. The control group initially recruited 35 participants, but only 33 completed the post-intervention assessment. Two participants were excluded from the analysis due to absence for over one-third of the sessions. The dropout rate for the control group was 8.57%. Both groups had dropout rates within the predetermined range of 15% set befor the study.

The study spanned 36 sessions from February 13th to May 31st, [insert year]. Data from participants who attended less than 12 sessions were

excluded from statistical analysis. Thus, statistical analysis was conducted on data from 30 participants in the experimental group and 33 participants in the control group.

Section 1: Participant Demographics

This study recruited a total of 70 participants, with 35 participants in both the experimental and control groups. Among them, 63 participants completed the entire study, with 30 participants in the experimental group and 33 participants in the control group. The average age of the experimental group (30 participants) was 77.7 years, with the majority being female (96.7%) and married (90.0%). See Table 4-1 for details. Assessment of demographic data in both groups showed no significant differences. Independent samples t-tests or Mann-Whitney U tests and chi-squared tests were used to analyze demographic data, revealing no significant differences between the two groups' demographic characteristics, as shown in Table 2.

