	protoct	posttast	difference	t value (p)	protost	nasttast	difference	t value (p)
	pretest	posttest	(Pre-test-P	或	pretest	posttest	(Pre-test-P	or
			ost-test)	S value (p)			ost-test)	S value (p)
	Mean ±	standard	deviation	-	Mean ±	standard	deviation	-
BMI	27.0 ± 3.5	26.9±3. 6	0.1±1.0	16.5 (0.741)	25.4 ± 3.8	25.3±3.7	0.1±0.4	75 (0.071)
30 seconds sit and stand	16.3±4.6	17.1±4. 4	-0.9±3.1	-56.5 (0.174)	17.7±5.2	18.5±4.9	-0.8±1.5	-83.5 (0.001)
The seat body bends forward (right)	96.0±20.7	121±25. 7	-26.6±31.2	-4.67(<0.001) §	92.5±25.4	98±20.2	-3.8±15.0	-1.47(0.151) §
The seat body bends forward (left)	2.9±10.1	7.3±9.6	-4.4±7.4	-140 (<0.001)	2.6±12.0	2.9±12.3	-0.3±2.8	0 (1.000)
Get up and walk Around at 2.4 meters	1.2±11.2	5.9±9.6	-4.9±8.1	-3.29 (0.003) §	1.4±13.4	2.9±13.2	-0.2±1.5	-0.79(0.433) §
Physiological quality of life	8.5±3.2	8.3±2.4	0.2±2.9	33 (0.507)	8.4±3.6	8.2±3.4	0.1±0.7	39 (0.384)
Psychological quality of life	10.8±1.4	11.1±1. 4	-0.1±0.4	-1.31 (0.202) §	11.4±1.5	11.3±1.4	0.0±0.1	1.00(0.325) §
Quality of social life	11.1±1.8	11.3±1. 7	-0.2±0.3	-18 (0.008)	11.7±1.8	11.7±1.9	-0.0±0.1	-0.5 (1.000)
Environment quality of life	11.2±1.9	11.3±1. 8	-0.1±0.4	-1.5 (0.500)	11.4±1.1	11.4±1.1	0.0±0.0	_*
The seat body bends forward (right)	10.6±2.2	10.6±2. 2	-0.0±0.1	-1.5 (0.500)	10.3±2.0	10.3±2.0	0.0±0.0	_*

§The Wilcoxon sign test is used, and the rest uses the dependent sample t test.

3. Comparison of Post-test between Experimental and Control Groups

Due to significant differences in demographic data and pre-test assessments between the experimental and control groups, particularly in the education level variable, and considering age as an important control variable, analysis of covariance (ANCOVA) was conducted to compare the post-test scores between the experimental and control groups. Age, education level, and pre-test scores were controlled for in the analysis. Intention-to-treat analysis was used.

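### The between-group ANCOVA is called intention-to-treat, but attendance and missing-test exclusions make it a completer analysis of 63 of 70 participants

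*Combined protocol and SAP*

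**What the plan says.** - **Exclusion rule.** Chapter 3, Section 2 (Research Participants) states that participants who take no physical "activity for more than three weeks or have missing pre-test or post-test data will be excluded from the statistical analysis".
- **Planned label.** Chapter 3, Section 6, item 2(d) plans an ANCOVA of post-test on group, adjusted for pre-test, and adds: "This analysis will utilize intention-to-treat principles".
- **Reported label.** Chapter 4, Section 2, item 3: "Intention-to-treat analysis was used". The covariates are given there too: "Age, education level, and pre-test scores were controlled for in the analysis".
- **Who was analysed.** The opening of the Research Results chapter says "statistical analysis was conducted on data from 30 participants in the experimental group and 33 participants in the control group", out of 35 recruited to each group. Tables 2 to 5 and 7 are headed N=30 and N=33. The same chapter also says "data from 70 participants who completed at least 30 sessions were analyzed".
- **Why people were dropped.** Five experimental participants missed more than one-third of the 36 sessions "due to health issues or personal preferences, rendering their data unusable". Two controls were dropped for the same degree of absence, with no underlying reason given.

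The documents describe no imputation or other method for missing data.

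**The concern.** An analysis that removes allocated participants because they attended poorly is not intention-to-treat. Attendance is known only after allocation and may be affected by the intervention, so removing people on that basis can undo the comparability that allocation was meant to give. Here the loss is uneven, and the reasons given in the experimental group (health, preference) could well relate to fitness and quality of life, which are the outcomes.

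The number 63 is disclosed, but the label tells readers that the comparison is protected from this selection when it is not. The ANCOVA carries the five between-group claims in the abstract. Two of them, psychological and environmental quality of life, are close to p = 0.05 and reappear in the conclusion.

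**Working it through.** **1. Counts.** 35 − 5 = 30 and 35 − 2 = 33, so 63 of 70 (90%), which reproduces the stated 30 and 33. Exclusion is 5/35 = 14.3% (printed 14.28%) in the experimental group and 2/35 = 5.7% in the control group. The printed 8.57% is 3/35.

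**2. Was the ANCOVA itself run on 63?** For a one-df group effect, partial eta² = F/(F + df), so df = F(1 − eta²)/eta². Outcomes are matched to Table 6 by the p-values in the text, because the row labels are displaced. Intervals allow for rounding of eta² to three decimals.

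| Outcome | F | eta² | df | interval |
|---|---|---|---|---|
| 2-minute step | 21.154 | 0.267 | 58.07 | 57.93–58.22 |
| Right sit-and-reach | 7.091 | 0.109 | 57.96 | 57.67–58.26 |
| Left sit-and-reach | 10.294 | 0.151 | 57.88 | 57.65–58.10 |
| Psychological | 4.766 | 0.076 | 57.94 | 57.53–58.36 |
| Environmental | 4.080 | 0.066 | 57.74 | 57.27–58.21 |

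The other five rows are less precise but all admit 58. Over all ten rows the intervals meet at 57.93–58.10, so the only integer is 58. That is 63 − 5 (intercept, group, age, education as one term, pre-test). With 70 participants the same model has df 65, or 62 with education as four dummies. F = 21.154 would then give eta² of 0.246 or 0.254, not 0.267.

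A second check is the experimental paired t for the 2-minute step (Table 5). −26.6/(31.2/√30) = −4.67, as printed; n = 35 would give −5.04.

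**3. Attendance rules.** Four statements do not agree:
- no activity for more than three weeks (Chapter 3, Section 2);
- absent from more than 12 of 36 sessions, so at most 36 − 13 = 23 attended (Results);
- fewer than 12 sessions attended (Results, possibly a translation slip);
- 70 analysed participants with at least 30 sessions each (Results), although seven of the 35 + 35 attended at most 23.

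**4. Possible bias.** Suppose the excluded differ from their own arm's completers by dE and dC SD. Then completer difference minus full difference = −(5/35)dE + (2/35)dC.
- Same shift in both arms, −1 to +1 SD: +0.086 to −0.086 SD.
- Independent shifts within −1 to +1 SD: extremes +0.143 + 0.057 = +0.20, and −0.20.

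The planned effect was 0.5 SD.

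**5. Tipping points.** Take t = √F, t_crit(58) = 2.0017 and SE ≈ √(1/30 + 1/33) = 0.2523 residual SD. The margin is (t − t_crit) × 0.2523. Divide it by 3/35 for the same shift in both arms, or by 5/35 if only the experimental losses shift.

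| Outcome | t | margin | same shift | experimental only |
|---|---|---|---|---|
| Environmental | 2.020 | 0.0046 | −0.05 | −0.03 |
| Psychological | 2.183 | 0.0458 | −0.53 | −0.32 |
| Right sit-and-reach | 2.663 | 0.1668 | −1.9 | −1.17 |
| Left sit-and-reach | 3.208 | 0.304 | −3.6 | −2.1 |
| 2-minute step | 4.599 | 0.655 | −7.6 | −4.6 |

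This keeps the completer SE, which suits missing post-tests. If all seven had observed post-tests (35 and 35, SE √(2/35) = 0.239, df 65, t_crit 1.997, same residual SD), the same-shift tipping points become −0.38 for environmental and −0.86 for psychological.

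**6. Environmental score.** The experimental entry −1.5 (p = 0.500) in Tables 5 and 7 fits a signed-rank statistic with zeros dropped and two changes of the same sign: S = 0 − 2·3/4 = −1.5, exact p = 2 × 1/4 = 0.500. On that reading two of 30 experimental scores changed and, by the Table 7 footnote, no control score did. Table 5's footnote assigns this row to the paired t-test, but its marks look reversed, since the −4.67 that it attributes to Wilcoxon is a paired t (step 2).

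**The case against.** The strongest case is that the analysed number is openly stated, the direction of bias is unknown, and most of the result is safe. Much of this stands.

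- **The fitness results hold.** The three fitness outcomes need shifts of about 1.9 residual SD or more in both arms. Assigning zero change to all seven and using an unadjusted t-test on the Table 5 change scores leaves p = 0.0012 (step), 0.008 (right reach) and 0.003 (left reach).
- **The −0.05 SD figure is the pessimistic one.** It keeps the completer SE. With all seven observed and no shift, the environmental p would fall to about 0.037.
- **An SD shift is a crude model for environmental quality of life**, which hardly varied. That weakness exists apart from the label. It does mean that the five excluded outnumber the two who appear to have changed.
- **A missing post-test is not the same as an attendance rule.** Only the latter directly contradicts analysis as allocated. The Results say that 33 of the 35 controls finished the post-intervention assessment, so the two control losses may have no post-test.
- **Deleting the exclusion rule now would be a change made after the results were known.**

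None of this rescues the label. Disclosure of 63 does not make the analysis intention-to-treat, and the documents themselves give poor attendance as the reason for dropping all seven.

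**Conclusion.** The concern holds. The exclusion rule and the intention-to-treat label contradict each other in the plan, and the reported ANCOVA is a completer analysis of 63 of 70. The Results state 63 directly. The df check confirms it, assuming the covariates listed in Chapter 4 with education entered as one term.

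The size of the bias cannot be known from the documents. Under shifts of up to 1 SD it lies within ±0.086 SD (same shift in both arms) or ±0.20 SD (independent shifts). These are unadjusted SD units, so they are not directly comparable with the residual-SD tipping points. The practical consequence falls on the psychological and environmental quality-of-life claims; the fitness claims are robust to this problem.

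If the 14 people lost between 84 and 70 had already been allocated, the analysed share is 63/84 = 75%. The documents do not give the timing.

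**What to change.** 1. State whether post-tests exist for each of the seven. For the between-group ANCOVA, drop the attendance-based exclusion and analyse every allocated participant with a post-test in the assigned arm. Record this as a change made after the results were known.
2. Where post-tests are missing, state the missing-at-random assumption and add a delta-adjusted sensitivity analysis, for example −1 to +1 residual SD set separately by arm, with tipping points. Imputing from pre-test, age and education alone is not enough: these are already the ANCOVA covariates, so it essentially returns the completer estimate.
3. Keep the 63-participant ANCOVA as a completer (per-protocol) analysis, with one attendance definition used in both Chapter 3, Section 2 and the Results.
4. If none of the seven has a post-test, replace the intention-to-treat wording in Chapter 3, Section 6 and Chapter 4, Section 2 with completer analysis. Qualify the psychological and environmental quality-of-life conclusions in the abstract, discussion and conclusion.
5. Correct control dropout to 5.7%, reconcile 84, 70 and 63, and say whether the 14 were lost before or after allocation.

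The cost is wording plus a small re-analysis. Without post-tests for the seven, only the relabelling and the sensitivity analysis are possible. Some estimates or p-values may become less favourable.

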The study spanned three months, with pre-tests conducted within the first two weeks befor the first session and post-tests within two weeks after the 36th session. Functional physical fitness and quality of life assessments were conducted for both groups befor and after each session. Upon completion of the overall program, the researchers provided comprehensive feedback on the study's results.

Exercise Protocol:

Both groups initially engaged in modal rate-intensity exercise. The experimental group underwent a 12-week intervention program, consisting of 3 sessions per week, totaling 36 sessions. Each session lasted 60 minutes and included the following components:

Warm-up exercises (10-15 minutes)

Main exercise activity (30 minutes)

Cool-down exercises (5-10 minutes), with a 10-minute break in between To mitigate potential risks associated with exercise training, blood pressure measurements were taken befor each session. Participants engaged in exercises under the guidance of research personnel. If participants felt unwell on a given day, they were allowed to skip the session. In case of any discomfort during the activity, the training was immediately halted.

Hardware and Software Setup:

The intervention utilized a touch-enabled 11-inch tablet computer loaded with the research game system, serving as the interface for participants to interact with the VR interactive game. A laptop computer facilitated the connection between the tablet and projector. The game content could only be downloaded and used on the tablet or Android smartphones. To allow elderly participants to see the game's effectiveness during the activity, the tablet was wirelessly connected to the laptop and projected onto a white wall in the same Wi-Fi environment.

Game Implementation:

The game design included four aircraft, each representing a participant in the group. Before starting the game, the game and sensors were paired via Bluetooth. The sensors were securely placed on the waist belt at the lumbar spine level. Participants underwent posture corrections, including left-right bending, forward bending, and backward leaning, to ensure accurate sensor data capture. Once all participants completed the calibration, the game training for that session began, with three game records per activity.

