After 12 weeks and 36 sessions of intervention using the virtual reality interactive game designed in this study, elderly participants were able to increase their willingness to engage in physical activity and social interaction through participation in the game, thereby expanding their interpersonal relationships and interactions with the community environment. The research results also revealed that the experimental group had significantly higher post-test scores in psychological well-being (p=0.033) and environmental well-being (p=0.048) compared to the control group. This aligns with literature suggesting that the quality of life of older adults is influenced by their health status, activities, and functional status. Active social participation and positive interactions with others can contribute to a satisfying and happy old age (Chen et al., 2018; Chou, 2020). Although virtual reality interactive games currently available on the market can target specific balance training for users, they are limited to single-player or multiplayer models. In contrast, the game software developed in this study allowed up to four elderly individuals to exercise simultaneously, forming a small group activity. At the end of each game, the results were provided, motivating participants to engage in the game through competition and evaluation among themselves. This not only satisfied their sense of honor but also encouraged them to continue participating in the game activities. From the 6th week onwards, the stability of elderly participants' engagement in the activities was

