generally established. They tended to form groups with friends to play the game and would inquire about and remind each other of the next activity time. Peer encouragement and invitations played a crucial role in sustaining their participation. Increase itionally, participants became more interested in the activity as they interacted with peers, forming friendships and forming small groups. Even those who were initially reluctant to participants due to peer invitations and increased interest. This program not only provided balance training for community-dwelling elderly but also created a pleasant and positive atmosphere through the design of virtual reality interactive games, promoting high engagement and focus on the activities. This is consistent with scholars' suggestions that community centers can increase participants' engagement and relaxation through the design of group activities, leading to changes in mood and stress relief during center activities (Chuang et al., 2021).

Figure 9: Presentation and ranking of scores after the elders participated in the activity

Section 4: Study limitations and Future Recommendations

Virtual reality interactive game training can utilize changes in position control and audiovisual stimulation to enhance activity performance, allowing the elderly to focus their attention on experiencing the game during training and strive to achieve game objectives. In this process, virtual reality interactive games provide a rich, stimulating, and challenging environment that helps maintain dynamic and static balance and agility. Most elderly participants in the study found this to be an enjoyable activity.

This study involved collaboration between a gaming company, a company providing hardware sensors, and participants in community activity programs to innovate a team-based game software suitable for the elderly. During the process, several limitations were identified: Sensor and Game Identification Pairing:The pairing of sensors and game identities via Bluetooth was random, leading to complaints from the elderly about the inability to select their preferred colors for their aircraft. Setup Process:Prior to activities, setting up the game required connecting a tablet to a laptop and projecting it onto a wall approximately 1 meter away. The colors of the four aircraft in the game were too similar, making it difficult for participants to identify their own color during rapid body movements.

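### The ANCOVA treats 63 people trained in small groups and classes as independent; even slight positive clustering would remove the environmental quality-of-life result and moderate clustering the psychological one

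*Combined protocol and SAP*

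**What the plan says.** Chapter 3, Section 4 (Game Implementation) describes a game for four players: "The game design included four aircraft, each representing a participant in the group". Scores are ranked after each session. Chapter 5, Section 3 says the software "allowed up to four elderly individuals to exercise simultaneously, forming a small group activity". Of the period from week 6 onwards it says of the participants: "They tended to form groups with friends to play the game". The same section credits peer encouragement with sustaining participation and offers social interaction as an explanation for the quality-of-life gains.

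Controls attended classes led by an instructor (Chapter 3, Section 4; Chapter 4). Participants came from two centres. The number and size of the classes, and how the arms were spread over the centres, are not given.

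The analysis is in Chapter 3, Section 6, item 2(d): "ANCOVA will be employed to compare the post-test scores between the experimental and control groups while controlling for pre-test scores". Chapter 4 adds age and education as covariates and reports that "statistical analysis was conducted on data from 30 participants in the experimental group and 33 participants in the control group". The threshold is p < 0.05. No term for playing group, class or centre, no cluster-robust error and no ICC appears anywhere.

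**The concern.** People who train together, compete with each other and choose friends as partners may end up with similar outcomes. The report itself presents this interaction as part of how the game works. If outcomes correlate positively within groups, 30 VR participants carry less information than 30 independent people. An ordinary ANCOVA then gives standard errors and p-values that are too small. The control classes and the two centres raise the same question.

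The quality-of-life results are the most exposed. Social interaction would act on them most directly, and their p-values, 0.033 and 0.048, sit just under the threshold. The Abstract and Chapter 6 both claim significant psychological and environmental improvement on the strength of them.

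**Working it through.** **Inputs.** F and partial eta squared (η²) come from Table 6. Its row labels do not line up with the outcomes, so rows were matched by the p-values in the text of Chapter 4, Section 2. Arm sizes are 30 and 33. Change SDs (VR, control) come from Table 5, matched in the same way: psychological 0.3, 0.1; environmental 0.1, 0.0; right reach 7.4, 2.8; left reach 8.1, 1.5; step 31.2, 15.0. Assumed: VR groups of m = 4, and every ICC value.

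**1. Reproducing the reported results.** Error df = F(1 − η²)/η². Psychological: 4.766 × 0.924/0.076 = 57.9. Environmental: 4.080 × 0.934/0.066 = 57.7. This matches 63 − 5 = 58 (intercept, group, age, education as one term, pre-test). F(1,58) then gives p = 0.033 and 0.048, as reported. Table 6 therefore treats 63 people as independent.

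**2. Room for variance inflation.** The critical F(1,58) is 4.007. Tolerated inflation is F/4.007: environmental 1.018, psychological 1.189, right reach 1.770, left reach 2.569, step 5.279.

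**3. ICC at which p reaches 0.05, clustering in the VR arm only.** Inflation = 1 + w(m − 1)ICC, where w is the VR arm's share of the variance of the difference. So ICC = (F/4.007 − 1)/(3w).
- Equal arm variances: w = (1/30)/(1/30 + 1/33) = 0.524.
- Table 5 variances: for psychological, w = (0.3²/30)/(0.3²/30 + 0.1²/33) = 0.908; environmental 1.00; right reach 0.885; left reach 0.970; step 0.826.

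| Outcome | ICC, Table 5 variances | ICC, equal variances |
|---|---|---|
| Environmental | 0.018/(3 × 1.00) = 0.006 | 0.018/(3 × 0.524) = 0.012 |
| Psychological | 0.189/(3 × 0.908) = 0.07 | 0.189/(3 × 0.524) = 0.12 |
| Right reach | 0.29 | 0.49 |
| Left reach | 0.54 | 1.00 |
| Step | never | never |

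**4. p-values over a range of ICC.** The small-df columns use equal variances and Satterthwaite df, with 7 df for eight assumed VR groups and 32 for controls. This gives about 22, 20, 18 and 16 df down the rows.

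| ICC | Psych., equal, 58 df | Psych., Table 5, 58 df | Psych., small df | Env., equal, 58 df | Env., Table 5, 58 df | Env., small df |
|---|---|---|---|---|---|---|
| 0 | 0.033 | 0.033 | 0.040 | 0.048 | 0.048 | 0.056 |
| 0.05 | 0.040 | 0.045 | 0.049 | 0.057 | 0.065 | 0.066 |
| 0.10 | 0.047 | 0.058 | 0.057 | 0.065 | 0.082 | 0.077 |
| 0.20 | 0.062 | 0.084 | 0.075 | 0.083 | 0.116 | 0.097 |

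On small df the psychological result crosses 0.05 at an ICC of about 0.058. At ICC 0.20, in the same three settings, right reach has p = 0.024, 0.036 and 0.034; left reach 0.007, 0.013 and 0.013; the step test 0.001 or less.

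Combining Table 5 variances with small df (about 8) is harsher. Psychological p is then 0.059 even at ICC 0. Right reach at ICC 0.20 has F = 7.091/(1 + 0.885 × 3 × 0.20) = 4.63 and p = 0.063. This stacks heavily rounded SDs on an assumed group count, so it is a stress case only.

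**5. If control classes cluster too** (same ICC in both arms, equal variances, 58 df). With two classes of 16.5, psychological p is 0.049 at ICC 0.02 and 0.075 at 0.05. With one class of 33, it is 0.064 at ICC 0.02, and right reach is 0.055 at ICC 0.05.

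**6. Type I error.** In 40,000 simulated trials (six VR groups of four, two of three, 33 independent controls), the unclustered test at nominal 0.05 rejected in 0.059, 0.068 and 0.083 of trials at ICC 0.05, 0.10 and 0.20.

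**The case against.** A reader might infer that the standard errors are certainly too small, that the VR arm is really eight clusters, and that both quality-of-life results collapse under modest clustering. The documents support none of these as stated.

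- No ICC is reported. Positive correlation is plausible but not shown, and ranked competition could push outcomes apart.
- Eight clusters is only 30/4, rounded up. The text says up to four players, sessions could be skipped, and grouping with friends is described as a tendency from week 6. Changing partners would dilute the correlation. With Table 5 variances, the psychological threshold rises from 0.07 for groups of four to 0.189/(2 × 0.908) = 0.10 for groups of three and 0.189/0.908 = 0.21 for pairs.
- On 58 df the psychological result survives ICC 0.05 under either variance assumption.

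Two further objections have force. The variance shares rest on SDs printed to one decimal: rounding in Table 5 moves the psychological threshold between about 0.064 and 0.084, and Table 7 prints the control SD as 0.0 rather than 0.1, which gives 0.063. Also, few scores changed. If S in Table 5 is a signed-rank statistic, S = −18 with p = 0.008 fits eight non-zero changes, all in one direction (8 × 9/4 = 18; 2/2⁸ = 0.008). Likewise S = −1.5 with p = 0.500 fits two (2 × 3/4 = 1.5; 2/2² = 0.5). A mixed model may have almost nothing from which to estimate an ICC for these outcomes.

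These points limit the size of the claim. They do not justify an unexamined assumption of independence.

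**Conclusion.** The concern holds conditionally. The analysis assumes independence where the delivery of treatment gives good reason to doubt it, and positive within-group correlation would make the reported p-values too small. The environmental result has almost no room for this. The psychological result is fragile rather than refuted: its threshold of about 0.06 to 0.12 depends on the arm variances and df used. The step test is secure in every VR-only setting tried. Both reach results hold at ICC 0.20 apart from right reach in the stress case, and right reach also weakens if controls formed one large class. All of this assumes VR groups of four and an ICC that the documents do not give. Control-class and centre clustering, for which no details are given, could matter as much as the playing groups.

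**What to change.** Keep the specified ANCOVA and add a cluster-aware sensitivity analysis: either a partially nested mixed model with small-sample df, or ANCOVA with small-sample cluster-robust standard errors. Use VR playing group, control class and centre wherever attendance or game records identify them. State how changing partners were handled, and report the ICC. The documents mention stored body-angle data and game records but do not say that these show who played with whom. If membership cannot be recovered, or the ICC cannot be estimated, report the Table 6 p-values over an ICC range such as 0 to 0.20. In the Abstract and Conclusion, do not present the environmental improvement as established, and describe the psychological result as fragile, unless they hold under this analysis.

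The cost is a check of the records, one re-analysis and a few changed sentences. The downside is slightly wider intervals and larger p-values.
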